## **NUMITOR study (Nummular headache Iberian study on the Treatments and Outcomes in Real-World setting) *statistical analysis plan***

Clinicaltrials number: NCT05475769

Document version 1.0.0 July 11, 2021

A descriptive analysis will be carried out presenting the ordinal qualitative and quantitative variables as frequency and percentage, and quantitative variables as mean and standard deviation, or as median and interquartile range based on the type of distribution. The normality of the distribution will be evaluated using the Kolmogorov-Smirnov test.

Statistical analysis will be performed primarily by intention to treat, but also an analysis per protocol will be carried out.

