### **Response rate:**

#### *Primary outcome:*

The main study variable will be the 50% response rate evaluated between weeks 8 and 12 of treatment, compared to the baseline. The baseline period will be defined as the month prior to the treatment onset.

For its calculation, the percentage of patients who present a reduction in the number of headache days per month of at least 50%, compared to the month prior to the start of treatment, will be calculated.

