**Response predictors:**

To assess which variables are associated with a greater probability of response, a logistic regression analysis will be performed in which the dependent variable will be the presence of a 50% response between weeks 8 and 12 of treatment.

First, a univariate logistic regression analysis will be carried out in which all study variables, demographic, clinical, and treatment-related will be evaluated. Those variables with a *P* value lower or equal to 0.2 will be included in a multivariate model.

A statistical significance level of 0.05 will be considered. For the adjustment for multiple comparisons, the adjustment according to False Discovery Rate will be used using the Benjamini-Hochberg method.

Statistical analysis will be performed using SPSS (IBM).

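### Does choosing between mean (SD) and median (IQR) with a Kolmogorov-Smirnov test misdescribe skewed variables?

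*SAP*

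**What the plan says.** The opening paragraphs of the SAP describe "quantitative variables as mean and standard deviation, or as median and interquartile range based on the type of distribution". The next sentence names how that distribution is judged: "The normality of the distribution will be evaluated using the Kolmogorov-Smirnov test". The SAP does not say whether the test is corrected for an estimated mean and SD, and it adds no plot or skewness criterion.

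The section on response predictors states "A statistical significance level of 0.05 will be considered". Carrying that level over to the normality test is a natural reading, but the SAP does not say so. The same section names SPSS as the software without a procedure or version, so the document cannot settle whether the corrected or the uncorrected test would be run.

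The primary outcome is a binary one: "The main study variable will be the 50% response rate evaluated between weeks 8 and 12 of treatment, compared to the baseline". The SAP gives no sample size.

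**The concern.** The standard critical values of the Kolmogorov-Smirnov test apply when the reference distribution is fully specified in advance. Here the plan supplies no mean or SD, so both must come from the data. The fitted normal curve then lies closer to the sample than the true one would, the test statistic shrinks, and the usual critical value is too large. A variable can be clearly skewed and still pass as normal.

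Because this is the only test named for choosing the summary, a skewed variable that passes would be reported as mean (SD). Headache days per month are a plausible case, since they cannot exceed the length of the month and may be asymmetric or pile up at that limit. The baseline description of the patients would then be less faithful than it could be. Shapiro-Wilk with a Q-Q plot, or simply reporting both summaries, would cost one sentence.

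**Working it through.** The SAP states no power or rejection rate for this test, so there is no figure of its own to reproduce. The check asks how often the test rejects, and then what depends on the answer.

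**Inputs.** From the SAP: the test, its role in choosing the summary, and the 0.05 level (assumed to apply here too). Assumed: sample sizes from 20 to 300 and the distributions below.

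**Statistic.** For an ordered sample x(1), …, x(n) with sample mean m and SD s, let F(i) = Φ((x(i) − m)/s). Then D is the largest value, over all i, of i/n − F(i) and F(i) − (i − 1)/n.

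- Uncorrected version: reject if D exceeds the exact 95% point for a fully specified null distribution.
- Lilliefors-type version: reject if D exceeds the 95% point of D simulated from normal samples with m and s estimated.

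There were 10,000 simulated samples per cell up to n = 100 and 4,000 above. A gamma variable has skewness 2/√shape, so shapes 16, 4 and 2 give 0.5, 1 and 1.41.

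**Rejection rates, uncorrected / Lilliefors-type:**

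| Distribution | n = 50 | n = 100 | n = 200 |
|---|---|---|---|
| Normal | 0.0% / 5.7% | 0.0% / 5.3% | 0.0% / 4.8% |
| Gamma, skewness 0.5 | 0.2% / 13% | 0.5% / 23% | 1.9% / 42% |
| Gamma, skewness 1 | 1.8% / 40% | 8.4% / 70% | 36% / 95% |
| Gamma, skewness 1.41 | 7.7% / 70% | 37% / 96% | 88% / 100% |
| Exponential, skewness 2 | 38% / 96% | 93% / 100% | 100% / 100% |
| Lognormal, sigma 1 | 81% / 99.5% | 99.8% / 100% | 100% / 100% |
| Headache days 1–30, beta-binomial (1, 2) | 3.1% / 58% | 25% / 95% | 89% / 100% |

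For comparison, Shapiro-Wilk in a separate run of 2,000 samples rejected skewness 1 in 69%, 96% and 100% of samples at n = 50, 100 and 200.

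**Reading the table.** The near-zero rate in the first row concerns normal data, where not rejecting leads to the right summary. Uncorrected, the test does miss mild skew at every size shown, and usually misses moderate skew at 50 to 100. It usually finds strong skew from about 100, and skewness of 1.41 by 200. It is therefore too strong to say that it almost never rejects. With the correction, skewness of 1.41 is usually detected at all three sizes, and skewness of 1 from n = 100.

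**What a wrong choice costs.** Take the assumed headache-day distribution. Beta(1, 2) has mean 1/3 and distribution function 1 − (1 − p)², so its median is 1 − √0.5 = 0.293. On the 1 to 30 scale the mean is 1 + 29 × 0.333 = 10.7 days and the median is about 1 + 29 × 0.293 = 9.5 days. Showing one instead of the other moves the reported centre by about 1.2 days in a descriptive table.

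**What depends on the test, section by section:**

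- Primary outcome: the proportion of patients whose headache days fall by at least half. Each patient is classified from their own counts, and no normality assumption enters.
- Secondary outcomes: further response rates at other thresholds and times, proportions with adverse effects and discontinuation, and the same in subgroups, with 95% confidence intervals. None uses the test.
- Response predictors: logistic regression, which does not require normally distributed covariates. Variables enter the multivariate model by their univariate P value, not by a normality test.

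The test's only role in the SAP is to choose the display format of quantitative variables.

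**The case for a change.** The strongest case for a change is that the plan names a specific method and leaves open a version that behaves badly. Two analysts could follow the sentence faithfully and differ: at skewness 1.41 and n = 100, one version rejects in 37% of samples and the other in 96%. In a separate run of 2,000 samples with whole-number headache days capped at 30 and about 23% of patients at the cap, the rates for uncorrected, Lilliefors-type and Shapiro-Wilk were 6%, 75% and 99% at n = 50. Headache days underlie the primary outcome, and the remedy is cheap.

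Three parts of this stand: the version is unspecified, the uncorrected form is a poor detector of moderate skew in small to moderate samples, and Shapiro-Wilk is the more powerful test.

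Two parts do not carry through. Headache days reach the primary outcome through a within-patient percentage reduction, so their summary in a baseline table has no bearing on it. And greater power is not the same as better description. The Lilliefors-type test already rejects a nearly symmetric 0–10 score (a normal variable with mean 6 and SD 2, rounded and limited to the scale) in 80% of samples at n = 50 and essentially all at n = 100, although mean (SD) would describe it well. Any significance test is a rough guide to the choice of summary. An analyst who looks at a visibly skewed histogram can report the median, and the plan's commitment to let the distribution decide supports that.

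**Conclusion.** The technical observation is right, but it does not call for a change to the plan. Uncorrected, with an estimated mean and SD, the Kolmogorov-Smirnov test has a rejection rate near 0% under normality and finds skewness of 1 in 1.8% to 36% of samples between n = 50 and n = 200. It does not follow that skewed variables will be shown as mean (SD). The SAP does not specify the uncorrected form, the corrected form has about 5% size and useful power, and strong skew is usually found at moderate sample sizes even without correction.

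The consequence is confined to the format of descriptive tables, about 1.2 days between mean and median in the illustrative headache-day distribution. No response rate, confidence interval, odds ratio or P value would differ. The rejection rates rest on assumed sample sizes and distributions, and on applying the 0.05 level to this test. The conclusion that no outcome analysis is touched rests on the SAP text alone. What is left is a small gap, the unnamed version of the test, which analysts can fill sensibly when they prepare the tables.

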#### *Secondary outcomes:*

In addition, the 50% response rate will be calculated between weeks 20 and 24, compared to the baseline situation, as well as the 75% and 30% response rates, both between weeks 8 and 12 and 20 and 24.

The proportion of patients experiencing adverse effects and discontinuing treatment because of them will be reported.

As study subgroups, the response and tolerability will be specifically evaluated in women and elderly patients, using the previously defined variables, in women, patients over 65 years of age and over 80 years of age.

All these variables will be presented with their corresponding 95% confidence intervals.

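### Does an intention-to-treat response rate measured in weeks 8 to 12 of treatment silently leave out patients who stop early?

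*SAP*

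**What the plan says.** The introductory paragraph of the SAP sets the analysis principle: "Statistical analysis will be performed primarily by intention to treat, but also an analysis per protocol will be carried out". Neither analysis set is defined there.

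Under Primary outcome, the endpoint is fixed as follows: "The main study variable will be the 50% response rate evaluated between weeks 8 and 12 of treatment, compared to the baseline". The reference period is anchored to the start of treatment: "The baseline period will be defined as the month prior to the treatment onset". The quantity to be computed is "the percentage of patients who present a reduction in the number of headache days per month of at least 50" per cent relative to that month.

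Under Secondary outcomes, the SAP adds the 50% rate at weeks 20 to 24 and the 30% and 75% rates in both windows. It also plans for stopping: "The proportion of patients experiencing adverse effects and discontinuing treatment because of them will be reported". That proportion is reported separately and is not linked to response status.

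Under Response predictors, the same endpoint is used again in a logistic regression: "the dependent variable will be the presence of a 50% response between weeks 8 and 12 of treatment".

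**The concern.** Read side by side, the analysis principle and the endpoint seem to pull apart. Intention to treat promises to count everyone who started. A window expressed in weeks of treatment can be taken to exist only for those still treated. A patient who stops in week 4, say, never reaches it, and the SAP does not say what value that patient receives.

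If the gap were filled by leaving such patients out, the primary percentage would be a rate among persisters. The SAP describes no comparison arm against which the effect could cancel. The primary and per-protocol results would come close together. The same would apply to the 30% and 75% rates, and the rate could rise from the first window to the second merely because non-responders had left. The predictor model would lose the same patients.

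**Working it through.** The SAP states no sample size, response rate or stopping rate, so it has no figure to reproduce. The check has two parts: how large the effect could be, and whether the text leads there.

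**Size under assumed values**

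Let r be the response rate among patients still treated in the window, d the share who stop before it, and q the response rate among stoppers. All three are assumptions.

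- Rate over all starters: r(1 − d) + q·d
- Rate among stayers only: r
- Difference: r − [r(1 − d) + q·d] = (r − q)·d

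With q = 0 and r = 0.50:

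| d | all starters, r(1 − d) | stayers only | difference |
|---|---|---|---|
| 10% | 45% | 50% | 5 points |
| 20% | 40% | 50% | 10 points |
| 30% | 35% | 50% | 15 points |
| 40% | 30% | 50% | 20 points |

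Over r from 0.40 to 0.70 and d from 5% to 30%, still with q = 0, the difference runs from 0.40 × 0.05 = 2 points to 0.70 × 0.30 = 21 points.

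These figures depend on q. For r = 0.50 and d = 20%:

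- q = 0: 0.50 × 0.80 = 40%, difference 10 points.
- q = 0.20: 0.40 + 0.20 × 0.20 = 44%, difference 6 points.
- q = r = 0.50: 0.40 + 0.50 × 0.20 = 50%, no difference.
- q = 1 (logical limit): 0.40 + 0.20 = 60%, so the stayers-only rate would be too low.

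Overstatement therefore needs two conditions: stoppers are dropped, and q < r.

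**What the text supports**

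Three readings are possible.

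1. All starters form the denominator, and a stopper who does not show the reduction is not in the numerator. This fits the stated principle and the wording of the calculation, and it gives r(1− d) when stoppers are counted as non-responders.
2. The window is a time label counted from treatment onset, the same anchor used for the baseline month, and headache days are observed in it whether or not treatment continues. This gives r(1 − d) + q·d and is also intention to treat.
3. Stoppers are dropped. This gives r, and it is the only reading at odds with the stated principle.

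No sentence in the SAP selects the third reading. Planning a per-protocol analysis as well suggests that the primary analysis is meant to keep patients whom the other one removes. Under Secondary outcomes, the weeks 20 to 24 window is named without any reference to being on treatment, so the supposed conflict is not even worded there.

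**The case for a change.** The best case for a change is that the missing step sits inside the primary endpoint. The SAP sets out how the percentage is calculated and stops short of saying who counts when treatment ends early. With no randomised comparison described, the handling of stoppers is most of what separates the two planned analyses. An analyst could choose among the readings after seeing the data. Standard logistic regression also omits cases with a missing dependent variable, so the model and the descriptive rate could rest on different patients. The planned 95% confidence intervals would not show any of this.

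It stands that no classification rule is written down and that one sentence would remove the doubt. It does not stand that the plan, followed as written, yields a wrong rate. A stopper counted as a non-responder has a defined value in both the percentage and the regression, so the two would agree.

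Nor is the obvious rule free of cost. Counting every absent record as a failure is itself a choice of what to estimate. If 10% of records were missing from patients who respond at the same 50% as the rest, the reported rate would be 0.50 × 0.90 = 45%, which is 5 points too low.

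**Conclusion.** No change to the plan is called for. The SAP leaves unwritten how early stoppers and patients without a count in the window are classified. Its stated principle and its definition of the percentage point to keeping all starters, and an intention-to-treat analyst would ordinarily fill the gap that way. The contradiction appears only if the window is read as open solely to patients still treated and the rest are then discarded, which the document does not say.

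Had stoppers been dropped, the excess would be (r − q)·d. That is 2 to 21 points under the assumed ranges with no response among stoppers, less if some of them respond, and zero if they respond as often as stayers. The SAP supplies none of r, q or d, so these numbers illustrate sensitivity and do not measure a bias in this plan.

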### **Response rate:**

#### *Primary outcome:*

The main study variable will be the 50% response rate evaluated between weeks 8 and 12 of treatment, compared to the baseline. The baseline period will be defined as the month prior to the treatment onset.

For its calculation, the percentage of patients who present a reduction in the number of headache days per month of at least 50%, compared to the month prior to the start of treatment, will be calculated.

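### Does setting a baseline month against the weeks 8–12 window move the 30%, 50% and 75% response thresholds?

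*SAP*

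**What the plan says.** The primary outcome section of the SAP sets the endpoint: "The main study variable will be the 50% response rate evaluated between weeks 8 and 12 of treatment, compared to the baseline". It then fixes the reference period: "The baseline period will be defined as the month prior to the treatment onset". The calculation is the percentage of patients with "a reduction in the number of headache days per month of at least 50%, compared to the month prior to the start of treatment".

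The secondary outcomes section adds the 50% response rate for weeks 20 to 24, and the 75% and 30% rates, "both between weeks 8 and 12 and 20 and 24". In the response predictors section, "the dependent variable will be the presence of a 50% response between weeks 8 and 12 of treatment".

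The SAP does not give the length of a month in days or the first and last day of each week-based window. It states no rule for turning a week-based count into a monthly figure. Equally, it does not say that unscaled counts from windows of unequal length are to be compared.

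**The concern.** Response is a ratio of two headache-day counts, so the windows behind them must be equal or the counts must be scaled. Here one window is named in months and the other in weeks. If the month is 30 or 31 days and the span from week 8 to week 12 is 28 days, a patient with daily headache and no change at all appears to improve. If weeks 8, 9, 10, 11 and 12 all count in full, follow-up is 35 days and the same patient appears to worsen.

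Under any one such reading the error is systematic, so a larger sample would not remove it. It would reach the primary endpoint, five secondary response rates (50% at weeks 20–24, and 30% and 75% at both windows), the response results in the subgroups, and the dependent variable of the predictor model.

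**Working it through.** The SAP gives no figure of its own to reproduce here. The check asks how far the thresholds would move under each reading of its text.

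**Inputs**
- Nominal thresholds r: 30%, 50% and 75% (primary and secondary outcomes sections).
- Baseline days B: one month, length not stated. Assumed 28, 30 or 31.
- Follow-up days F: weeks 8 to 12. Assumed (12 − 8) × 7 = 28, or 5 × 7 = 35 if all five weeks count. Weeks 20 to 24 work the same way.

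**If raw counts are compared.** A patient responds when the follow-up count is at most (1 − r) times the baseline count. In terms of daily headache rate, the true reduction needed is 1 − (1 − r) × B/F.

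| B vs F (days) | nominal 30% | nominal 50% | nominal 75% |
|---|---|---|---|
| 28 vs 28 | 30.0% | 50.0% | 75.0% |
| 30 vs 28 | 25.0% | 46.4% | 73.2% |
| 31 vs 28 | 22.5% | 44.6% | 72.3% |
| 30 vs 35 | 40.0% | 57.1% | 78.6% |

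For example, with 30 vs 28 days and r = 50%: 1 − 0.5 × 30/28 = 1 − 15/28 = 46.4%.

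A patient with daily headache and no change would show an apparent reduction of 1 − 28/30 = 6.7% or 1 − 28/31 = 9.7%. With 35 days, 1 − 35/30 = −16.7%, an apparent increase.

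**If each count is put on a common scale** (count × 28 / days observed), B and F cancel and the reduction needed equals r, whatever the window lengths.

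**Effect on the 50% response rate, two illustrations**

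1. Assume every patient has headache on all 30 baseline days and a follow-up daily probability that is uniform across patients, so the follow-up count is uniform on 0 to F.
   - F = 28: raw 16/29 = 55.2% against scaled 15/29 = 51.7%, a difference of +3.4 points.
   - F = 35: raw 16/36 = 44.4% against scaled 18/36 = 50.0%, a difference of −5.6 points.
   - Equal windows: 0 points.
2. Assume headache on 50% of baseline days, days independent, and a true halving, so the patient sits on the cut-off. The probability of being classed a 50% responder is 0.547 (28 vs 28), 0.618 (30 vs 28), 0.652 (31 vs 28) and 0.373 (30 vs 35). For the same patient with no true change it is 0.011 (28 vs 28) and 0.018 (30 vs 28), so the effect is concentrated near the cut-off.

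For a patient with 10 baseline headache days, the 50% cut-off is 5 days. Scaling from 30 to 28 days gives 10 × 28/30 × 0.5 = 4.67, a move of one third of a day.

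**Which row does the text support?** The definition of response is worded as a frequency per month on both sides of the comparison, which points to a common scale. The follow-up windows each span four weeks, the nearest whole-week equivalent of a month, which points to 28 vs 28. Nothing in the SAP selects 30 or 31 vs 28 on an unscaled basis, and counting five full weeks is the less natural reading of the window.

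**The case for a change.** The strongest case for a change is that this SAP takes on the definition itself. It sets the baseline period and says how the percentage is calculated, so the detail cannot simply be assigned to the protocol. Naming a monthly unit is not a conversion rule. Two analysts could follow the text, one counting 30 or 31 baseline days against 28 and the other rescaling, and report different primary results. One sentence would prevent that.

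Part of this stands. The month length and boundary days are not written down, and the arithmetic for unscaled counts is correct. The 75% threshold would move too, though less than the others.

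What does not stand is the step from an unstated length to a biased endpoint. It requires the analyst to take a calendar month, ignore the monthly scale in the definition of response, and divide counts from windows known to be unequal. The document asks for none of these. The readings also disagree on direction, and the most natural ones give no shift.

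**Conclusion.** The concern does not require a change. The shift depends on unscaled counts from unequal windows, which the SAP does not specify. By reading, the effect on the 50% response rate is +3.4, −5.6 or 0 points in the illustration with daily baseline headache and a uniform follow-up probability. The SAP supports neither of those two assumptions. With a four-week month, or with both counts expressed per month, the effective thresholds are exactly 30%, 50% and 75%.

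What is left is a missing definition of a familiar kind. Its sensible completion is plain from the text: equal four-week windows, or a monthly rate on both sides. The exact days of a diary window are also commonly set in the protocol, which is not shown. The conclusion assumes that the analyst follows the monthly scale in the response definition. It would change only if the analysis were found to divide raw counts from windows of different length.

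### Response is a percentage of one month's headache-day count, but the predictor model neither guarantees baseline frequency a place nor requires a flexible form for it, so markers of low frequency can pass as response predictors

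*SAP*

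**What the plan says.** Under Primary outcome, the main variable is "the 50% response rate evaluated between weeks 8 and 12 of treatment, compared to the baseline". It is calculated as "the percentage of patients who present a reduction in the number of headache days per month of at least 50%, compared to the month prior" before treatment. The reference is one month: "The baseline period will be defined as the month prior to the treatment onset". Under Secondary outcomes, the 50% rate is repeated at weeks 20 to 24, and the same baseline serves the other cut-offs: "as well as the 75% and 30% response rates, both between weeks 8 and 12 and 20 and 24". The only breakdowns named there are by sex and age: "in women, patients over 65 years of age and over 80 years of age". None is by baseline headache frequency.

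Under Response predictors, the dependent variable is the 50% response at weeks 8 to 12. In the univariate step "all study variables, demographic, clinical, and treatment-related will be evaluated". Entry to the next step follows one rule: "Those variables with a *P* value lower or equal to 0.2 will be included in a multivariate model". No variable is exempt from that rule, and no functional form is stated for quantitative variables. The significance level is 0.05, with Benjamini-Hochberg adjustment for multiple comparisons.

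**The concern.** The baseline count is the denominator of the outcome, so it is part of how response is constructed. A patient with few headache days can halve the count through ordinary month-to-month variation; a near-daily patient almost cannot. At very low counts the three cut-offs also run together, because days are whole numbers.

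Two things follow. The overall rate depends partly on the mix of baseline frequencies, and the planned tables would not show this. In the predictor analysis, baseline headache days is treated like any other candidate. It may fail the screen, or it may enter as one straight-line term. Either way, sex, age, clinical form or treatment choice could be named as a predictor of response only because it goes with fewer headache days.

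**Working it through.** The SAP gives no sample size, frequency distribution or expected rate, so there is no planned figure to reproduce. Everything numerical below rests on stated assumptions.

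**Step 1: whole-day cut-offs.** With baseline b, a cut-off c means at most floor(b(1 - c)) days at follow-up.
- b = 1: the 30%, 50% and 75% limits are 0.7, 0.5 and 0.25, so all three mean 0 days.
- b = 2: the limits are 1.4, 1 and 0.5, so 30% and 50% both mean at most 1 day.
- b = 4: the limits are 2.8, 2 and 1, so 30% and 50% both mean at most 2 days.

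**Step 2: chance response with no true change.** From the SAP: the 50% criterion, a one-month baseline and a 4-week window. Assumed: 28 days in each period, independent counts in the two periods with the same mean m, at least 1 baseline day, and within-patient correlation rho of 0 (binomial) to 0.1 (beta-binomial). With p(b) the probability of b days and F its cumulative sum,

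chance(m) = [sum over b >= 1 of p(b) x F(floor(b/2))] / [1 - p(0)].

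| Mean days per 28 | rho = 0 | rho = 0.05 | rho = 0.1 |
|---|---|---|---|
| 2 | 35.9% | 49.8% | 58.2% |
| 4 | 20.5% | 32.9% | 40.5% |
| 8 | 7.7% | 18.4% | 25.0% |
| 15 | 0.7% | 5.6% | 10.7% |
| 20 | 0.0% | 1.3% | 3.9% |
| 25 | 0.0% | 0.1% | 0.5% |

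**Step 3: case mix.** At rho 0.1, chance response is 31.2% at 6 days and 0.5% at 25. If 20%, 50% or 80% of patients are at 6 days and the rest at 25, the overall chance rate is w x 31.2 + (1 - w) x 0.5, or about 6.7%, 15.8% and 25.0% (from unrounded inputs).

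**Step 4: the predictor procedure.** Simulation of the P <= 0.2 screen followed by the multivariate logistic model. Half the patients have a mean of 5 days and half 20. A binary factor has no effect given frequency, but is commoner in the low-frequency half. It is tested at 0.05 *before* Benjamini-Hochberg. Entries are percentages of runs at n = 100 / 200 / 400. The bands column forces baseline in as bands (a flexible term did about as well where tried).

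| Setting (factor prevalence, low vs high frequency) | Baseline passes screen | Factor significant: screen as written | Baseline forced in, linear | Baseline forced in, bands |
|---|---|---|---|---|
| All improve 30%, rho 0.1, 60% vs 30% | 30 / 34 / 49 | 9 / 14 / 24 | 10 / 14 / 23 | 7 / 10 / 16 |
| All improve 30%, rho 0.05, 70% vs 30% | 42 / 62 / 82 | 12 / 15 / 33 | not shown | about 8 / 8 / 13 |
| No change, rho 0.1, 60% vs 30% | 80 / 96 / 100 | 9 / 16 / 29 | not shown | 7 / 15 / 22 |

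An independently coded repeat moved single entries by up to six points and left the pattern unchanged. Over the settings tried, the written screen gave about 6% to 45%. In the worst no-change case, bands lowered 45% only to 36%. A single linear term gives no real gain, so the functional form matters at least as much as the screen.

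**Step 5: when it does not matter.** In a similar two-cluster set-up with no change and rho 0.1, a factor unrelated to frequency was significant in 4.3% of runs at n = 150. With a weak link (50% vs 40%) the figures were 4.4%, 4.6% and 6.8% at n = 80, 150 and 300.

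**Step 6: Benjamini-Hochberg.** With 15 candidates, 13 of them noise (an assumption), rho 0.1 and a 60% vs 30% link, the factor was significant after adjustment in 0.8%, 0.6% and 4.2% of runs at n = 100, 200 and 400 under a uniform 30% improvement (7%, 12% and 23% before it), and in 0.4%, 2.5% and 7.4% under no change. With a 70% vs 30% link, 9-14% remained at n = 400.

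**The case against.** Four arguments on the other side carry weight.

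*Baseline days is already a candidate.* It would presumably be screened as a clinical variable. That stands: the SAP does not exclude it, and with no true change it usually passes. But entry is not guaranteed, and a linear term does not solve the problem once it has entered.

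*The size depends on what the SAP does not give.* Sample size, frequency mix and day-to-day variability are unknown, and a protocol that is not shown may restrict baseline frequency. This stands too. The absence of a minimum baseline count from a SAP is not a fault in itself, since eligibility is commonly left to the protocol. A minimum would not remove the gradient: requiring at least 8 observed days still leaves 38.7% at a true mean of 8 days against 0.5% at 25 (rho 0.1).

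*The stated aim is association.* A factor that tracks low frequency really is associated with this response, so reporting it is not false. That is correct, but a multivariate model is read as separating such explanations, and here it may fail to.

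*Multiplicity is adjusted.* Benjamini-Hochberg lowers the rates markedly, as shown above. It does so by raising the threshold, not by removing the confounding. A reader might take the unadjusted percentages as error rates of the written plan; they are not.

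**Conclusion.** The point holds in moderate form. Chance response falls from about 20-40% at 4 days to 8-25% at 8 and 0-4% at 20, assuming 28-day months, no true change and rho 0 to 0.1. The predictor analysis gives baseline frequency no assured place and no flexible form. Before multiplicity adjustment, a factor with a moderate to strong link to frequency then appears as a predictor in about 6-45% of simulated runs at n = 100-400, given 5-day and 20-day clusters. The rate is lower after adjustment. The effect is small if nearly all patients have near-daily pain or the link is weak.

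A reader might infer that the primary rate is invalid or largely chance, or that forcing baseline in would clear the bias. The document supports neither. The frequency mix is not given, the responder definition can stay, and adjustment for a noisy one-month count only reduces the bias.

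**What to change.** 1. Under Response predictors, state that baseline headache days per month is always included in the multivariate model, exempt from the P <= 0.2 screen, as a spline or in pre-set bands rather than one linear term. Add that residual confounding remains, because a one-month count measures a patient's usual frequency with error.
2. Under Primary outcome and Secondary outcomes, report the 30%, 50% and 75% response rates with 95% confidence intervals by pre-set baseline-frequency bands, beside the overall rate. The overall rate stays primary. The document offers no basis for particular cut-points, so the sponsor should choose and justify them before the data are examined.

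A sensitivity analysis restricted to patients with, say, at least 8 observed baseline days is not advised. Selecting on the observed count adds regression to the mean: at a true mean of 8 days and rho 0.1, chance response rises from 25.0% to 38.7% among those retained.

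The cost is SAP wording, one table, two or three model degrees of freedom, and wider intervals within bands. No new data are needed, since the baseline count already enters the primary outcome.
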